## 4 STUDY DESIGN

### 4.1 OVERALL DESIGN

**Study Design:** This behavioral trial will use a two-arm randomized controlled design. Each of the 60-90 care partner participants will be randomized to an active “JITAI” arm (n=10-15 care partners of SCI, n=10-15 care partners of HD, n=10-15 care partners of HCT) or to a control arm (n=10-15 care partners of SCI, n=10-15 care partners of HD, n=10-15 care partners of HCT). The random allocation of participants to the treatment arm or control arm establishes the basis for testing the statistical significance or difference between the groups.

**Randomization:** Blocked randomization will be used to limit bias and achieve an equal distribution of participants to the control and treatment arms. A randomization list will be generated for each condition (SCI, HD, HCT) and the study statistician will oversee randomization. The participant will be randomized once he/she is deemed eligible and has provided informed consent (i.e. at enrollment prior to baseline data collection). The study coordinator/research assistant who consented the participant will use the appropriate condition’s randomization list to assign the participant to the correct study arm.

**Duration of Study Participation:** Study participation for both arms of the study (control and JITAI) involves a baseline assessment, followed by an approximate 10-day run-in period then a 3-month (90 day) home monitoring period (in which the intervention will be administered to the JITAI group). Thus, the total duration of the study is ~100 days.

**Study Sites:** This is a single-site study at the University of Michigan.

**Study Intervention:** The just in time adaptive intervention (JITAI) uses sensor data derived from the Fitbit® (e.g., accelerometer-based estimates of physical activity and sleep) and real-time self-report ratings (assessed once daily) of HRQOL (caregiver strain, depression, anxiety) to deliver personalized “pushes” to participants via a study specific app (CareQOL app). The personalized pushes will be delivered on ~50% of the days over the 3-month intervention period.

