## 6.2 FIDELITY

For this study, the intervention will be administered via the CareQOL app. The study team will conduct training during the baseline visit with each participant which will include:

- Helping the participant download and register for the CareQOL and Fitbit® apps on their personal device
- Helping the participant set any relevant app settings (e.g., make sure alerts are turned on/off, privacy settings, etc.)
- Demonstrating the CareQOL app features to the participant (e.g., participant dashboard, etc.)

- Ensuring that the participant understands the importance of entering the daily ratings and wearing the Fitbit®
- Explaining the relationship between the daily ratings and Fitbit® data and the intervention prompts (JITAI group only)
- Demonstrating how to sync the Fitbit® (including using the Fitbit® app) and how to enter the daily ratings in the CareQOL app

During the 10-day run-in period between the baseline visit and the start of the intervention, study team members will assist participants to make sure that participants can:

- Successfully wear and sync the Fitbit®
- Successfully respond to the EMA prompts

Participants who are unable to successfully complete the run-in period will be terminated from the study and noted as a screen failure.

Training and training materials will be provided to all study team members. New study members will undergo training before the study is started. Training will be documented in the electronic regulatory binder.

Participant adherence to the protocol will be assessed throughout the study. Study staff will have access to the CareQOL app dashboard which can be used to monitor participant engagement and adherence with the app. Specifically, study staff will monitor:

- Adherence to EMA entry
- Adherence to Fitbit® use/syncing
- Adherence to completing the end of month surveys (~30, 60, 90 day)

Adherence will be calculated as a percentage for each of these areas for all participants who are not withdrawn or lost to follow-up.

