### **8.1.2 CARE PARTNER ELIGIBILITY**

Confirmation of care partner eligibility according to criteria listed in Section 5, above, will be documented on the Eligibility CRF. It will occur prior to informed consent being obtained and before any study procedures associated with baseline assessment. Eligible individuals will then participate in the consent process, followed by randomization and baseline data collection.

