## 9.2 SAMPLE SIZE DETERMINATION

The main purpose of the current trial is to establish the feasibility and acceptability of an intensive data collection protocol in order to inform the a larger, later-stage effectiveness study on the JITAI in care partners of persons with chronic medical conditions. Thus, the current study is designed to provide a point of estimate for the effect of the JITAI for this future large-scale trial. Given that there are no formal power analysis calculations for this type of analysis, we have based the proposed sample size on our previous experience conducting these types of trials. Specifically, we believe that ~50 participants will provide sufficient numbers and diagnostic diversity to evaluate feasibility and acceptability of new mobile health apps. Thus, or sample size of N=60 caregivers (30 per arm and 20 per care partner group), exceeds this estimate and should provide a reasonable range of scores on the HRQOL outcome measures to guide later phase trial work.

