## 9.3 POPULATIONS FOR ANALYSES

The primary endpoint will examine survey responses on the feasibility and acceptability questionnaire that is designed to evaluate our intensive data collection protocol in the full sample (i.e., N=60 care partners). Secondary endpoints will include attrition and adherence estimates (again across the full sample). Exploratory analyses will be conducted to identify trends for an improvement in HRQOL scores (i.e., strain, depression, and anxiety) for care partners that are randomized to the intervention group. These analyses will also look for a trend for an improvement in the remaining HRQOL scores for care partners that are randomized to the intervention group, and will compare the JITAI group with the control group on all of the different HRQOL measures. Exploratory analyses may also compare important subgroups (e.g., caregiver groups that differ by diagnosis [SCI, HD or HCT], relationship type [parent vs. spousal caregivers], caregiver groups that differ by sex [male vs. female caregivers], caregiver groups that differ according to the functional status of the person with TBI (e.g., complicated mild vs. moderate vs. severe TBI or perceived functional status based on Mayo Portland Adaptability Index scores). Exploratory analyses will be an intention-to-treat approach where the participant will contribute data to the arm he/she was randomized to regardless of the amount of data contributed (i.e. the duration of participation).

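### The staff member who takes consent assigns the arm from the randomization list, and no allocation concealment is described, which leaves the exploratory arm comparison open to selection bias

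*Combined protocol and SAP*

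**What the plan says.** The Randomization paragraph of section 4.1 sets the method: "Blocked randomization will be used to limit bias and achieve an equal distribution of participants to the control and treatment arms". On the lists it says: "A randomization list will be generated for each condition (SCI, HD, HCT) and the study statistician will oversee randomization". On the act of assignment it says: "The study coordinator/research assistant who consented the participant will use the appropriate condition’s randomization list to assign the participant to the correct study arm".

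The order of steps is fixed in two places. Section 4.1: "The participant will be randomized once he/she is deemed eligible and has provided informed consent". Section 8.1.2: "Eligible individuals will then participate in the consent process, followed by randomization and baseline data collection".

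Two passages give the arm comparison a use. Section 9.3 says the exploratory analyses "will compare the JITAI group with the control group on all of the different HRQOL measures". Section 9.2 says that "the current study is designed to provide a point of estimate for the effect of the JITAI for this future large-scale trial".

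The document does not state the block size, whether it is fixed or varied, who holds the lists, or whether the person assigning can see later rows.

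**The concern.** Allocation is concealed when the person who decides on enrolment cannot know the next assignment. Here that person is told to work from a list generated in advance. Oversight by the statistician does not say who can open the list. Randomizing after consent fixes the sequence for one participant, but it does not hide the next row from someone choosing which candidate to approach, or whether to wait a week.

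There is a second route even if later rows are hidden. Staff know past assignments, because they made them and because section 6.2 reserves one part of the baseline training for the JITAI group. If the block size is fixed and known, past assignments reveal some future ones.

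At stake is the comparability of the arms at entry. If candidates are timed or deferred with the next arm in view, the between-arm difference in strain, depression or anxiety mixes selection with any effect of the messages. That estimate is then carried into the planning of the larger trial. The primary and secondary hypotheses in section 9.1 are stated regardless of group assignment and section 9.3 analyses them in the full sample, so they do not rely on comparable arms.

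**Working it through.** **1. Is concealment supplied anywhere?**

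| Section | What it provides | Does it hide the next assignment? |
|---|---|---|
| 4.1 | Blocked lists by condition, statistician oversight, consenting staff assign | No; custody and block size not stated |
| 8.1.2 | Eligibility, then consent, then randomization | No; fixes order only |
| 5.2 | Second exclusion criterion is an open judgement | No; leaves discretion |
| 5.5 | Several recruitment sources, no fixed order of contact | No; leaves room for timing |
| 10.1.1.2 and 10.1.6.1 | REDCap for consent and data capture | No randomization function mentioned |
| 10.1.5 | A manual of procedures | Not cited for randomization and not supplied |

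**2. How predictable is a fixed block?** The block size is an assumption. Take a 1:1 block of size m, with past arms known. An assignment is certain once one arm is used up, so the number of certain assignments equals the length of the final run. Counting all sequences:

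- m = 2: the second is always certain, 1/2 = 50%.
- m = 4: of 6 sequences, 2 end in a run of two and 4 in a run of one. (2×2 + 4×1)/(6×4) = 8/24 = 33%.
- m = 6: of 20 sequences, 2 end in a run of three, 6 in a run of two and 12 in a run of one. (6 + 12 + 12)/(20×6) = 30/120 = 25%.

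**3. How large could the bias be?** The plan has no figure to reproduce here. Inputs:

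- SD = 10, the reference SD of the T metric (section 8.1.5).
- n = 30 per arm (section 9.2), or 3 × 15 = 45 per arm at the upper limit in section 4.1.
- Assumed: correlation r between baseline and month 3 of 0.5 to 0.6, with 0.3 to 0.8 as a wider range.
- Assumed: 3 participants per arm whose baseline differs by 10 points. This is a high-end value, because baseline scores are collected after randomization and staff could steer only on impressions.

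Formulas, with change from baseline as the endpoint (section 3):

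- Baseline shift per arm = 3 × 10/n, doubled if the arms are steered in opposite directions.
- Shift in the difference in change = baseline shift × (1 − r), since the fraction r persists to month 3.
- SD of change = 10 × √(2(1 − r)), and SE of the arm difference = SD of change × √(2/n).

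| n per arm | Steering | r | Shift in change | SE | Shift/SE |
|---|---|---|---|---|---|
| 30 | both arms | 0.5 | 2.0 × 0.5 = 1.0 | 2.58 | 0.39 |
| 30 | both arms | 0.6 | 2.0 × 0.4 = 0.8 | 2.31 | 0.35 |
| 30 | one arm | 0.5 | 1.0 × 0.5 = 0.5 | 2.58 | 0.19 |
| 30 | one arm | 0.6 | 1.0 × 0.4 = 0.4 | 2.31 | 0.17 |
| 45 | both arms | 0.5 | 1.33 × 0.5 = 0.67 | 2.11 | 0.32 |
| 45 | both arms | 0.6 | 1.33 × 0.4 = 0.53 | 1.89 | 0.28 |
| 30 | both arms | 0.3 | 2.0 × 0.7 = 1.4 | 3.06 | 0.46 |
| 30 | both arms | 0.8 | 2.0 × 0.2 = 0.4 | 1.63 | 0.24 |

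**4. Effect on a test.** Assume a two-sided 5% test and no true effect. The rejection probability at a shift of d standard errors is Φ(d − 1.96) + Φ(−d − 1.96).

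- d = 0.17: Φ(−1.79) + Φ(−2.13) = 0.037 + 0.017, about 5.3%.
- d = 0.46: Φ(−1.50) + Φ(−2.42) = 0.067 + 0.008, about 7.5%.

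**The case against.** The strongest reply is that silence is not exposure. The statistician oversees randomization, and the manual of procedures may say how the list is held. Eligibility is recorded before consent, and most criteria in section 5.1 are factual. Staff have no baseline scores to steer on. The arm comparison is exploratory, the exploratory hypotheses in section 9.1 concern decreases within the JITAI group, and section 9.4.4 plans a comparison of the arms at baseline. The illustrated bias is under half a standard error on inputs that are nearly all assumed. If staff impressions track stable severity rather than the score of the day, the bias in a change score is smaller still. The block figures need a fixed size that staff know, and the plan states neither.

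Much of this stands, and it limits the point. The documents do not show that anyone can see later rows, so what is established is that concealment is not described. The comparison is secondary to the purpose of the trial, and the likely bias is small.

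It does not remove the point. Section 4.1 gives a working rule that places the list with enrolling staff, and neither oversight nor the order of steps hides the next entry. Factual criteria do not prevent timing or deferral. A baseline comparison can show a measured imbalance but does not correct it, and candidates who were passed over have no scores to examine.

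**Conclusion.** The concern holds. As written, section 4.1 lets the person who enrols use the list that assigns, and no other section supplies concealment. The conclusion is about the described procedure; it is not a finding that bias has occurred or that concealment is known to be absent.

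With 30 per arm and r of 0.5 to 0.6, the illustrated shift in the arm difference is 0.4 to 0.5 points if one arm is steered and 0.8 to 1.0 points if both are (0.17 to 0.39 SE). Over r of 0.3 to 0.8 the two-arm case is 0.4 to 1.4 points (0.24 to 0.46 SE). These figures rest on the assumed correlation, number steered and 10-point difference. The harm is confined to the exploratory comparison and the effect estimate for the later trial. That makes this a worthwhile, inexpensive correction rather than a threat to the main result.

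**What to change.** Replace the assignment sentence in section 4.1 with text such as:

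*The three condition lists are held by the study statistician or in a REDCap randomization function. One assignment is released at a time, after eligibility and consent have been recorded. Enrolling staff cannot see later assignments. Block sizes vary at random and are not disclosed to enrolling staff.*

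If the manual of procedures already conceals the list, say so in section 4.1 instead.

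REDCap is already used for consent and data capture, but the documents do not show that its randomization function is available; release by the statistician needs no new system. The cost is a short set-up or 60 to 90 single releases, plus the replaced text. The order of consent, randomization and baseline stays as it is, as do training and participant burden.

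The January 2021 amendment entry on over-recruiting suggests that enrolment may have started. If so, apply the change to the remaining enrolments, record the date, and describe separately how earlier participants were assigned.

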## 4.2 END-OF-STUDY DEFINITION

The end of the study is defined as the completion of the 3-month home monitoring period, specifically the end of month questionnaires (occurring at 90 days +/- 7 days).

## 5 STUDY POPULATION

### 5.1 INCLUSION CRITERIA

In order to be eligible to participate in this study, an individual must meet all of the following criteria:

1. Provide informed consent
2. Be at least 18 years of age
3. Be able to read and understand English
4. Provide emotional, physical, and/or financial support/assistance to the individual with SCI/HD/HCT, indicating a response ≥1 to the following question: “On a scale of 0-10, where 0 is

“no assistance” and 10 is “assistance with all activities”, how much assistance does the person you care for require from you to complete activities of daily living due to problems resulting from his/her SCI/HD/HCT? Activities could consist of personal hygiene, dressing and undressing, housework, taking medications, managing money, running errands, shopping for groceries or clothing, transportation, meal preparation and cleanup, remembering things, etc.”

5. Have access to necessary resources for participating in a technology-based intervention (smartphone/tablet and internet access) and be willing to use their personal equipment/internet for this study, including downloading the study app and the Fitbit® app on their mobile device
6. Is able and willing to complete all study assessments for the duration of their study participation (approximately 100 days)
7. **Care partners of persons with HD:** Be caring for an adult (18 years or older) with a clinical diagnosis of HD. Medical documentation of the HD is required.
8. **Care partners of persons with SCI:** Be caring for an adult (18 years or older) that is  $\geq 1$  post-injury and sustained a medically documented SCI. Medical documentation of the SCI is required.
9. **Care partners of persons with HCT:** Be caring for an adult (18 years or older) who is receiving, has received or is scheduled to receive HCT. Medical documentation of the HCT is required.

## 5.2 EXCLUSION CRITERIA

An individual who meets the following criteria will be excluded from participation in this study:

1. Is a professional, paid caregiver (e.g., home health aide)
2. Anything that would preclude safe or meaningful participation in the study

## 5.3 LIFESTYLE CONSIDERATIONS

During this study, participants are asked to:

- Wear a Fitbit® 24 hours/day, except when charging during the 10-day run-in period and 3-month (90 day) home monitoring period.
- Install the CareQOL app and Fitbit® app on their personal mobile device, and keep these apps installed for the duration of the study (~100 days).

## 5.4 SCREEN FAILURES

Screen failures are defined as participants who consent to participate in this study but are not subsequently assigned to the study intervention or entered in the study. Screen failures are unlikely in this study because eligibility assessment occurs pre-informed consent. However, if during the 10-day run-in period before the 3-month home monitoring period starts the study team is made aware of something that would change their eligibility, the participant will be noted as a screen failure.

## 5.5 STRATEGIES FOR RECRUITMENT AND RETENTION

**Recruitment:** All recruitment activities will take place at University of Michigan (U-M). Recruitment and retention methods used in this study will be approved by the IRBMED and are detailed in the IRBMED submission. Potential participants will be recruited directly or through the person they are caring for.

**SCI Recruitment:** The study team will primarily recruit through clinical databases (e.g., Data Direct and EMERSE) and participant registries, including the CODA registry and Spinal Cord Injury Model Systems registry. Participants may also be recruited through outreach to SCI community groups and organizations.

**HD Recruitment:** The study team will primarily recruit through clinical databases (e.g., Data Direct and EMERSE) and participant registries, including the CODA registry and the Enroll-HD study, where participants opt to be contacted about participating in future research studies (both the CODA registry and Enroll-HD have individuals with HD and their care partners). Participants may also be recruited through outreach to HD community groups and organizations.

**HCT Recruitment:** The study team will recruit participants using several methods. Participants will be recruited through the U-M Blood and Marrow Transplantation Program (BMT); weekly meetings are held where patients are considered for clinical trials/research studies. Clinical databases (e.g., Data Direct and EMERSE) will be used for recruitment. The Long-Term Follow-Up Biorepository will also be used for recruitment. Lastly, participants may be recruited from the Outpatient BMT clinic and through outreach to BMT health care providers and community engagement partners.

Individuals who are interested in participating will be encouraged to ask questions about the study and their participation, and if they opt to enroll, they will provide informed consent prior to completing any study assessments.

In order to ensure that recruitment targets are being met, teleconference calls with the study recruitment teams by the project manager will be conducted to review progress, discuss problems, and guide additional recruitment efforts to meet stratification goals.

**Retention:** Given the intensive nature of this study, we expect that participants will miss some daily assessments and have times when they do not wear the Fitbit®; our retention plan is focused on minimizing these missed assessments and engaging participants throughout the study.

Retention will be facilitated by several strategies:

- App development will consider factors known to increase participant engagement including strategies to target engagement and minimize fatigue (easy to navigate platform, app tailoring based on Fitbit® sensor feedback, etc.). The app will also include a study team dashboard that we will use to monitor participant engagement.
- User guides and contact information for the study team (phone and email) will be supplied to participants and they will be encouraged to contact the study team with any questions or concerns.

- When enrolling participants, we will offer participants a choice of wristbands; they can select the wristband that is most comfortable and visually appealing to them. If they are not happy with their selection, we will provide an alternate wristband.
- Study staff will maintain regular contact with the study participants. All study participants will be contacted at least once during the study run-in period, at least once during the first week of the 3-month home monitoring period and at least once each month during the remaining months of the 3-month home monitoring period.
- Participants who do not complete any study assessments (e.g., uploading Fitbit® data or answering EMAs) for several days will receive a reminder from the study team.
- In case of lost equipment/equipment failure during the run-in and home monitoring periods, we will send replacements as supplies allow.

**Participant Incentives:** We will compensate participants for their time and inconvenience, as follows:

- Baseline assessment: Participants will receive \$20 for completing this assessment (\$20 total possible).
- Monthly HRQOL surveys during the home monitoring period: Participants will complete end of month surveys during the home monitoring period. Participants will receive \$10 for completing each end of month survey for months 1-3 (\$30 total possible).
- Daily EMA assessments and Fitbit® data during the 3-month home monitoring period: Participants will receive \$1 per day for each day that they have EMA and/or Fitbit® data during the three-month (90 day) home monitoring period (\$90 total possible).
- Participants who complete the study will be allowed to keep the Fitbit® that they use in the study.
- Compensation will occur monthly to encourage prompt responding.
- We may send out nominal value items (e.g., notepads, pens) throughout the duration of study participation to encourage engagement.

